6.1 Changes to the Planned Efficacy Analysis Proposed in Protocol

The protocol called for interim analyses when three patients will be enrolled and complete through full EZN-2279 pharmacokinetic sampling (Week T-9) and again when six patients complete through 9-weeks of EZN-2279 dosing. There will be a third look that will be used for a Biologics License Application (BLA). In addition, there will be a final analysis (fourth look) to be completed on all patients on EZN-2279 after one year (i.e. two maintenance cycles).

6.2 Primary Endpoint and Analysis

The primary endpoint is the proportion of patients achieving metabolic detoxification, assessed from trough dAXP samples obtained at Weeks T-15, T-17, T-19, and T-21. Metabolic detoxification is defined as a trough dAXP concentration equal to or below 0.02 µmol/mL.

Trough dAXP level will be summarized at each above time point. Maintenance of detoxification is defined as meeting the target trough levels for each of the 4 weeks listed above in the EZN-2279 treatment period. The proportion of patients meeting this definition of maintenance will be summarized.

Trough dAXP level will be summarized at last observed value as a sensitivity analysis using the as-treated population.

6.3 Secondary Endpoints and Analysis

Data regarding blood sample collections for trough samples, lymphocyte subset, and quantitative immunoglobulins will be listed but not summarized.

6.3.2 Maintenance Phase Trough Plasma dAXP and ADA Activity

Maintenance phase trough plasma dAXP and ADA activity will be assessed from trough plasma dAXP and ADA samples obtained during the maintenance phase of the study (every 3 months following T-21) through completion of EZN-2279 maintenance treatment period. Trough dAXP and ADA levels will be summarized at each time point during the maintenance period. Maintenance of adequate trough dAXP and ADA levels is defined as meeting the target trough levels for both dAXP and ADA at each visit during the maintenance period. The proportion of patients meeting this definition of maintenance will be summarized.

6.3.3 Immune Status

Immune Status will be assessed through completion of the EZN-2279 maintenance period, through assessment of:

- Absolute lymphocyte count
- B-, T-, and NK-lymphocyte subset analysis: The number of cells for each subset will be determined by FACS using the following panel:
 - Percent and Absolute CD3+ (Mature T cells)
 - Percent and Absolute CD3+ CD8+ (Suppressor T Cells)
 - Percent and Absolute CD3+ CD4+ (Helper Cells)
 - Percent and Absolute CD (16+56)+ (Natural Killer Cells)
 - Percent and Absolute CD19+ (B Cells)
 - Absolute Lymphocytes (CD45+)
 - %CD4 (Helper Cells) / %CD8 (Suppressor T Cells)
- Quantitative immunoglobulin concentration (IgG, IgA, IgM)

Summary statistics for immune status variables will be presented at baseline, each intermediate collection time-point, and endpoint. Immune status values and changes from baseline to each visit and endpoint will be summarized using descriptive statistics. The frequency of clinically significant abnormal values will be summarized for selected immune status variables using descriptive statistics.

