#### **6.2.2. Secondary Objectives**

The secondary objectives of this study are to:

- Evaluate the safety and tolerability of EZN-2279
- Assess the immunogenicity to EZN-2279 and Adagen®, including binding antibodies, neutralizing antibodies and anti-PEG antibodies
- Evaluate whether therapy with EZN-2279 maintains trough plasma ADA activity  $\geq 15 \mu\text{mol/h/mL}$

- Determine the PK profile of EZN-2279
- Assess the effect of EZN-2279 on immune status as determined by absolute lymphocyte count, lymphocyte subset (B, T, and NK) analysis, and immunoglobulin (Ig) concentration (IgG, IgA, IgM)
- Compare the clinical status (infections and hospitalizations) of the patients during the EZN-2279 treatment period compared to the prior six months
- Assess the clinical growth status of the patients during the EZN-2279 treatment and maintenance periods

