### **9.3. Exclusion Criteria**

Patients meeting any of the following exclusion criteria will not be eligible for enrollment.

1. Autoimmunity requiring immunosuppressive treatment.
2. Patients with detectable neutralizing anti-Adagen® antibodies at screening evaluation.
3. Severe thrombocytopenia (platelet count  $< 50 \times 10^9/\text{L}$ ).
4. Current participation in other therapeutic protocols for ADA-deficient combined immunodeficiency.

5. Current or prior participation in another clinical study with an investigational agent and/or use of an investigational drug in the 30 days before study entry.
6. Known planned participation in a gene-therapy study for the planned duration of this study.
7. Any condition that, in the opinion of the PI, makes the patient unsuitable for the study.
8. Inability or unwillingness to administer Adagen® or EZN-2279 on a one time per week regimen.
9. Inability to comply with the study protocol.
10. Female patients who are pregnant or lactating.
11. Female patients who are breast-feeding.
12. Female patients of childbearing potential who are not using an FDA approved birth control method.

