##### **9.4.2. Concurrent Treatments**

Concurrent treatments intended to directly treat the patient's disease are disallowed.

Concurrent treatments intended to prevent or treat complications associated with ADA-SCID (e.g., antibiotics, antifungal agents, intravenous immunoglobulins) are permitted.

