### 10.8. Recording of Concomitant Medications

All changes in prior and new prescription and non-prescription medications (including i.v. immunoglobulins, blood products, use of vitamins, supplements and herbal remedies) from the start of screening through the final study visit are to be recorded. For each change in prior medication and new medication the following will be recorded:

- Name of the medication
- Total daily dose
- Route of administration
- The start and stop dates
- The indication for use
  - If a product is being taken for the prevention of a condition, “prophylaxis for” or “prevention of” should be included in the description of indication
  - If a product is being taken for an active condition, a corresponding medical condition must be included in the medical history

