2.2 Secondary Objectives

- Evaluate the safety and tolerability of EZN-2279
- Assess the immunogenicity to EZN-2279 and Adagen[®], including binding antibodies, neutralizing antibodies and anti-PEG antibodies
- Evaluate whether therapy with EZN-2279 maintains the trough plasma ADA activity ≥ 15 $\mu\text{mol/h/mL}$
- Determine the PK profile of EZN-2279
- Assess the effect of EZN-2279 on immune status as determined by absolute lymphocyte count (ALC), lymphocyte subset (B, T, and NK) analysis, and immunoglobulin (Ig) concentration (IgA, IgG, IgM)
- Compare the clinical status (infections and hospitalizations) of the patients during the EZN- 2279 treatment period compared to the prior six months
- Assess the clinical growth status of the patients during the EZN-2279 treatment and maintenance periods

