10.4 Screening, Baseline and Study Weeks

No windowing schemes will be applied to the data. For by-visit summaries, if there are multiple assessments at a post baseline visit then the last non-missing assessment at that visit will be used for the summary. This includes assessments at the scheduled and unscheduled visits. For Patients who withdraw from the study, data at the early termination visit will be excluded from the by-visit summaries but will be included in the endpoint summaries.

Screening is defined as the last measurement for a variable before the initial dose of Adagen[®] study drug. With the exception of adverse events and medications, assessments collected at the screening visit are associated with the screening period because Adagen[®]

is not administered until all procedures are complete. Adverse events and medications starting on the day of the first dose of Adagen[®] are associated with Adagen[®] treatment.

Baseline is defined as the last measurement for a variable before the initial dose of EZN-2279 study drug, and is only used as the starting point for efficacy endpoints. With the exception of adverse events and concomitant medications, assessments collected at EZN-2279 Day-1 (Week T-1) are associated with Adagen[®] treatment because EZN-2279 is not administered until all procedures are complete. Adverse events and concomitant medications starting on the day of the first dose of EZN-2279 are associated with EZN-2279 treatment.

With regard to screening and baseline determination, assessments falling exactly on the date of the first dose of each study medication will be considered pre-dosing for that medication with the exception of adverse events and concomitant medications, which will be associated with the respective study drug.

Missing data will not be imputed.

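### SAP 6.3.3 summarises IgG over all patients as an effect of EZN-2279 and ignores permitted immunoglobulin replacement, so IgG in a replaced patient cannot be read as that patient's own production

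*SAP*

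**What the plan says.** - **Objective.** Protocol 6.2.2 sets out to "Assess the effect of EZN-2279 on immune status as determined by absolute lymphocyte count", lymphocyte subsets and immunoglobulin concentration. SAP 2.2 repeats this and names IgA, IgG and IgM.
- **Analysis.** SAP 6.3.3: "Immune status values and changes from baseline to each visit and endpoint will be summarized using descriptive statistics". It also counts clinically significant abnormal values for selected immune variables, without naming them. Replacement is not mentioned.
- **Baseline.** SAP 10.4: "Baseline is defined as the last measurement for a variable before the initial dose of EZN-2279 study drug". For immunoglobulins this is the Week T-1 sample. No visit windowing is applied.
- **Replacement allowed.** Protocol 9.4.2: "Concurrent treatments intended to prevent or treat complications associated with ADA-SCID (e.g., antibiotics, antifungal agents, intravenous immunoglobulins) are permitted". Nothing in Protocol 9.3 excludes patients on replacement; the nearest criterion is "Autoimmunity requiring immunosuppressive treatment".
- **Replacement recorded.** Protocol 10.3 takes medications and dose regimens from the 60 days before enrolment. Protocol 10.8 then records changes and "new prescription and non-prescription medications (including i.v. immunoglobulins, blood products", with total daily dose, route, start and stop dates and indication.
- **Use of those records.** SAP 7.8 gives frequencies by therapeutic class and preferred term, separately for the Adagen and EZN-2279 periods. Nothing ties them to IgG.

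**The concern.** The IgG summary is part of the planned answer to a stated objective, and Protocol 5.5 also treats immune function as an important aspect of safety. Infused IgG is measured together with the patient's own, and the SAP has no step that separates them.

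Two misreadings follow. Own production could fall after the switch while measured IgG stays near its baseline level. Or measured IgG could move because replacement was started, stopped or re-dosed, or because the sample fell at a different point between infusions, with no change in the patient. A start of replacement after the switch may itself signal worsening immunity, yet in a change-from-baseline table it could appear as an IgG gain. With about six patients, one such patient can weigh heavily on a mean.

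**Working it through.** The plan states no figure for IgG, so there is nothing to reproduce. The check has four steps.

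**1. What a change in IgG contains.** Measured IgG = own + infused, so measured change = change in own + change in infused.
- No replacement: the second term is zero and the planned summary is interpretable.
- Stable replacement, sampled at the same point in the cycle: the second term is again zero, but a percentage fall is diluted. If a share s of baseline IgG is infused, a fall of x% in own IgG shows as (1 − s)·x%. At s = 1/2 it is halved. The level is also held up.
- Replacement started, stopped or re-dosed: the second term is not zero. It can cancel or exceed the first.

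**2. Where the samples fall in an infusion cycle.** Sampling days come from Protocol 11.3 and 11.4: T-1 = Day 1, T-9 = Day 57, T-21 = Day 141. Maintenance Weeks 34, 47 and 60 are Days 232, 323 and 414 (Week T-1 counted as Week 1, since 21 + 13 = 34). Shift relative to baseline = (day − 1) mod cycle length. Cycle length is an assumption.

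| Sample | Days after T-1 | Shift, 28-day cycle | Shift, 21-day cycle |
|---|---|---|---|
| T-9 | 56 | 0 | 14 |
| T-21 | 140 | 0 | 14 |
| Week 34 | 231 | 7 | 0 |
| Week 47 | 322 | 14 | 7 |
| Week 60 | 413 | 21 | 14 |

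T-9 and T-21 have a window of ± 1 day. Maintenance visits have ± 3 weeks, which can place a sample anywhere in either cycle.

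**3. How large a timing artefact could be.** Assumptions: first-order decay at steady state, half-life h of 20 to 40 days, own production unchanged. A sample taken d days earlier in the cycle than baseline raises the infused part by 2^(d/h) − 1. One taken d days later lowers it by 1 − 2^(−d/h).
- From just before to just after an infusion, 21-day cycle: 2^(21/40) − 1 = 44% to 2^(21/20) − 1 = 107%.
- The same, 28-day cycle: 2^(28/40) − 1 = 62% to 2^(28/20) − 1 = 164%.
- The 14-day shift at T-9 and T-21 on a 21-day cycle has a sign that depends on where baseline fell. Baseline within the first 7 days after an infusion puts the later sample 14 days further on: a fall of 1 − 2^(−14/40) = 22% to 1 − 2^(−14/20) = 38%. A later baseline puts the sample 7 days earlier in the cycle: a rise of 2^(7/40) − 1 = 13% to 2^(7/20) − 1 = 27%.

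These percentages concern the infused part only. The effect on total IgG is s times as large, and the documents do not give s.

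**4. Effect on a six-patient mean.** If one patient's total IgG rose by an assumed 60% for such a reason, the mean percentage change would move by 60/6 = 10 points.

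**The case against.** The strongest reply is that this is one item within one descriptive secondary objective, beside lymphocyte counts, subsets, IgA and IgM. SAP 6 plans no tests, and the primary endpoint is untouched. SAP 6 and 7 list all efficacy and safety data, SAP 7.8 already summarises concomitant medication separately for the two drug periods, and patient profiles are planned in SAP Appendix C, whose content is in a companion document. With six patients, a careful reader could set IgG against replacement patient by patient.

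Much of that stands, and it limits the point. Four stronger readings are tempting but unsupported:
- *That four-weekly infusions distort the T-9 and T-21 changes through timing.* Those samples lie exactly 2 and 5 cycles of 28 days after baseline, so on a strict cycle the shift is zero apart from the visit window.
- *That IgG is counted among the abnormal values whatever the replacement.* SAP 6.3.3 limits that count to selected variables and does not say that IgG is one.
- *That the replacement data go unused.* They are summarised by drug period; the link to IgG is what is missing.
- *That IgG cannot inform the objective at all.* That depends on how many patients are replaced, and at zero the problem disappears.

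The reply does not remove the gap. The planned summary still combines replaced and unreplaced patients, and reading it correctly is left to whoever cross-checks the listings.

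**Conclusion.** The point holds in a limited form. Followed exactly, SAP 6.3.3 can show an IgG change, or hide one, for reasons unrelated to EZN-2279 in any patient on replacement. Masking and the effect of a start, stop or dose change do not depend on infusion timing. The timing artefact is conditional: nil at T-9 and T-21 on a strict 28-day cycle, possible with other intervals, with drift, and at maintenance visits.

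The overall size is unknown. It rests on the number of replaced patients (0 to 6 of 6), the infused share of IgG, the infusion interval and the half-life, none of which the documents give. This affects interpretation of one secondary measure and leaves the primary endpoint as it is. It is worth correcting because the remedy is cheap.

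**What to change.** Amend SAP 6.3.3, with no change to clinical management:

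1. Present IgG values and changes from baseline by replacement status: none; stable since before baseline; started, stopped or changed after baseline. Derive status from the Protocol 10.3 and 10.8 records. State that IgG under replacement is not read as own production. For a patient with none at baseline who later starts, show IgG up to the start and report the start. Do not simply restrict the summary to patients who stay unreplaced: someone whose IgG falls and who then starts replacement would leave it, biasing it towards stability.
2. Use IgA and IgM in all patients as the main humoral measures. This assumes that the infused product contributes essentially IgG, which the documents do not describe.
3. Tabulate patients who start, stop or change replacement after T-1 beside the IgG results.
4. If IgG is one of the variables selected for abnormal values, flag values taken under replacement.
5. List days since last infusion only where the date is available. Protocol 10.8 asks for start and stop dates, not each infusion date, so under stable replacement this may not be derivable.

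The cost is SAP wording and a small amount of extra programming to link medication and laboratory data. The downside is small subgroups, possibly with few or no patients whose IgG is interpretable.

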6.3.4 Clinical Status

Clinical status will be assessed through the conclusion of the EZN-2279 maintenance treatment period, through assessment of:

- Infections determined and defined as either:
 - Clinically documented – patients with documented signs and symptoms of infection without positive microbiologic cultures
 - Microbiologically documented - patients with documented signs and symptoms of infection and with positive viral or bacterial cultures
- Hospitalizations - incidence and duration of hospitalizations
- Change in growth – height, weight and growth curve determinations while patients are 18 years of age and younger
- Overall survival – through the EZN-2279 maintenance phase

The total number of infections and the incidence and duration of hospitalizations during the EZN-2279 treatment period will be summarized. Summary statistics for height, weight and BMI percentiles will be presented at baseline, each intermediate collection time-point, and endpoint. Percentiles will be calculated programmatically based on reported age, gender, height and weight.¹ Percentile scores and changes from baseline of percentile scores to each visit (at which height and weight are assessed) and endpoint will be summarized using descriptive statistics.

The proportion of patients surviving through the EZN-2279 maintenance phase will be summarized.

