#### 6.3.2. Secondary Endpoints

The secondary endpoints for efficacy are:

- Trough Plasma ADA Activity - will be assessed from trough plasma ADA samples obtained at Weeks T-15, T-17, T-19, and T-21. Adequate trough ADA activity will be defined as ADA activity  $\geq 15 \mu\text{mol/h/mL}$ .
- Maintenance phase trough plasma dAXP and ADA activity - will be assessed from trough plasma dAXP and ADA samples obtained during the maintenance phase of the study through completion of EZN-2279 treatment
- Immune Status – will be assessed through completion of the EZN-2279 maintenance period, through assessment of:
  - Absolute lymphocyte count
  - B-, T-, and NK-lymphocyte subset analysis: The number of cells for each subset will be determined by FACS using the following panel:
    - CD3+ (Mature T cells)
      - Percent and Absolute
    - CD3+ CD8+ (Suppressor T Cells)
      - Percent and Absolute
    - CD3+ CD4+ (Helper Cells)
      - Percent and Absolute
    - CD (16+56)+ (Natural Killer Cells)
      - Percent and Absolute
    - CD19+ (B Cells)
      - Percent and Absolute

- Absolute Lymphocytes (CD45+)
- %CD4 (Helper Cells) / %CD8 (Suppressor T Cells)
- Quantitative immunoglobulin concentration (IgG, IgA, IgM)
- Clinical status – will be assessed through determination of the following parameters
  - Infections through completion of the EZN-2279 treatment period will be determined and defined as either:
    - Clinically documented – patients with documented signs and symptoms of infection without positive microbiologic cultures
    - Microbiologically documented – patients with documented signs and symptoms of infection and with positive viral or bacterial cultures
  - Hospitalizations – Incidence and duration of hospitalizations through completion of the EZN-2279 treatment period compared to the 6-month period prior to study entry
  - Growth – height, weight and growth curve determinations through completion of the EZN-2279 maintenance period
  - Overall survival – will be assessed at the conclusion of the EZN-2279 treatment period through the end of EZN-2279 maintenance

The secondary endpoints for safety are:

- Safety – will be assessed through determination of adverse events (AEs), serious adverse events (SAEs), physical examinations, laboratory evaluations, and immunogenicity through completion of the EZN-2279 maintenance period.

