5.4 Disease Background and History

Disease background will also be summarized at screening. Missing categories will be presented if applicable. Disease background includes ADA-SCID diagnosis and current dose of Adagen[®], prior treatments for SCID including Adagen[®], prior Adagen[®] toxicities in the past year, infectious complications, and hospitalizations.

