6. EFFICACY ANALYSIS

The completer population will be used for the primary efficacy analysis, because the endpoint cannot be evaluated until T-21, and the as-treated population will be used for a sensitivity analysis of the primary efficacy endpoint. The as-treated population will be used for all other efficacy analyses, unless otherwise noted. Summaries will only be presented for the EZN-2279 group. Efficacy is evaluated in comparison to the Adagen® Lead in period ('baseline'). All efficacy data will be listed.

Given the sample size, all efficacy analyses will be descriptive (i.e., no statistical testing and no reported p-values), although 95% confidence intervals (CI) may be presented to show the variability of estimates.

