10.2 Association with Study Drug

Assessments collected at EZN-2279 Day 1 (Week T-1) are associated with Adagen[®] treatment because EZN-2279 is not administered until all procedures are complete. All endpoints are measured in comparison to screening or the Adagen[®] Lead -in phase (baseline), as appropriate, within each patient.

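### The objective of comparing infections and hospitalisations with the prior six months is not carried into either analysis section, and raw counts would cover unequal time

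*SAP*

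**What the plan says.** **The objective.** Protocol 6.2.2 reads "Compare the clinical status (infections and hospitalizations) of the patients during the EZN-2279 treatment period compared to the prior six months". SAP 2.2 carries the same objective, ending "treatment period compared to the prior six months".

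**The endpoint.** For hospitalisations, Protocol 6.3.2 reads "Incidence and duration of hospitalizations through completion of the EZN-2279 treatment period compared to the 6-month period prior to study entry". The infection endpoint in the same section names no comparator.

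**The analysis.**
- Protocol 13.2.3.4 lists infections and hospitalisations among the mainly descriptive secondary endpoints and names no comparison period.
- SAP 6.3.4 says "The total number of infections and the incidence and duration of hospitalizations during the EZN-2279 treatment period will be summarized".
- SAP 6 begins its comparator sentence "Efficacy is evaluated in comparison to the Adagen" and goes on to name the lead-in period as baseline. It also limits efficacy summaries to the EZN-2279 group.
- SAP 10.2 is looser: "All endpoints are measured in comparison to screening or the Adagen" lead-in, whichever is appropriate, within each patient.
- SAP 6.1, where efficacy changes are declared, lists only analysis looks, the last being a "final analysis (fourth look) to be completed on all patients on EZN-2279 after one year (i.e. two maintenance cycles)".

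**The pre-study data.** Protocol 10.3 and 11.1 collect infections and hospitalisations over the past 12 months. SAP 5.4 summarises disease background at screening, including "toxicities in the past year, infectious complications, and hospitalizations", with no six-month restriction and no link to SAP 6.3.4.

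**The concern.** In this single-arm study each patient is his or her own control, and for these two outcomes the pre-study period is the control that the objective names. The SAP text summarises one side of the contrast in SAP 6.3.4 and a differently defined history in SAP 5.4. It does not bring them together on a common window or per unit of time.

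A reader who sets the two summaries side by side would compare periods of different length. The treatment period is also not fixed: under Protocol 11.3.8.1 a dose adjustment sends the patient back to Week T-5 for four more weeks. If the window and anchor are chosen only at reporting, they are chosen after open-label data have been seen, which is easily avoided.

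**Working it through.** The documents state no infection or hospitalisation rate and no precision for this comparison, so there is no figure of the plan's own to reproduce beyond the calendar: Week T-21 falls on Day 1 + 7 × 20 = 141, as scheduled.

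**Inputs from the documents**
- EZN-2279 treatment period: at least 21 weeks, 21 × 7 = 147 days (Protocol 7.1.1).
- Each return to Week T-5: 28 more days (Protocol 11.3.8.1).
- Look-back: six months in the objective, 365.25 / 2 = 182.625 days; 12 months as collected, 365.25 days.
- Lead-in: at least 21 days (Protocol 7.1.1).
- Six evaluable patients (Protocol 13.1).

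**Step 1. Count ratio at an unchanged rate = treatment days / look-back days**

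| Treatment period | Days | Against six months | Against 12 months |
|---|---|---|---|
| No repeat | 147 | 147 / 182.625 = 0.80 | 147 / 365.25 = 0.40 |
| One repeat | 175 | 175 / 182.625 = 0.96 | 175 / 365.25 = 0.48 |
| Two repeats | 203 | 203 / 182.625 = 1.11 | 203 / 365.25 = 0.56 |

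Counted only to the Day 141 visit, the no-repeat ratio is 141 / 182.625 = 0.77.

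**Step 2. Size against chance.** Event rates are assumed at 0.5, 1 and 4 per patient-year, equal in both periods. Expected count in six patients = 6 × rate × days / 365.25. The SD of the difference is the square root of the sum of the two expected counts (Poisson).

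| Assumed rate | 21 weeks | Six months | Gap | SD of gap |
|---|---|---|---|---|
| 0.5 | 1.21 | 1.50 | 0.29 | 1.65 |
| 1 | 2.41 | 3.00 | 0.59 | 2.33 |
| 4 | 9.66 | 12.00 | 2.34 | 4.65 |

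The six-month gap stays at or below about half an SD. If the 12-month history were used uncut, the gaps would be 1.79, 3.59 and 14.34 events with SDs of 2.05, 2.90 and 5.80, that is 0.9, 1.2 and 2.5 SD.

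**Step 3. What patient-time does.** Six patients contribute 6 × 0.5 = 3.00 patient-years in six months and 6 × 147 / 365.25 = 2.41 in 21 weeks. At a constant rate of 2 per patient-year the expected counts are 6.00 and 4.83, and both divide back to 2.0 per patient-year. The artefact of unequal length disappears.

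**Step 4. The lead-in as comparator.** At its minimum the lead-in is 21 / 147 = one seventh of the treatment period and gives 6 × 21 / 365.25 = 0.34 patient-years. At 1 event per patient-year, 0.34 events are expected.

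**Step 5. Anchor.** The medication-history item in Protocol 10.3 equates enrolment with the start of lead-in. If study entry means that date, the six-month window ends at least 21 days before the first EZN-2279 dose: 21 / 182.625 = 11% of the window.

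**The case against.** The case against is substantial, and much of it stands.

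- **A reader might infer that the SAP silently dropped a planned analysis.** The documents do not support that. Protocol 13.2.3.4 names no comparator either, and SAP 6.3.4 follows it. The mismatch starts inside the protocol, between its objectives and its analysis section.
- **A reader might infer that there is no window or anchor at all.** The six months is in SAP 2.2 and Protocol 6.3.2, and the latter ties it to study entry for hospitalisations. What is missing is a calendar date for study entry and any use of the window in the analysis text.
- **A reader might infer that the objective cannot be answered.** SAP 5 and SAP 6 promise listings of study population and efficacy data, and patient profiles are planned. With about six patients these supply most of the raw within-patient information. Mock displays are in a companion document and the BLA analysis has its own SAP; neither was available, and either could contain such a table.
- **The lead-in baseline may not be meant for event counts.** SAP 10.4 defines baseline as a last measurement, which suits laboratory values, and SAP 10.2 allows screening where appropriate. This softens the conflict with SAP 6 but does not settle the comparator.
- **Larger figures are available but weakly grounded.** An anchor shift of 49 days needs study entry to mean the start of a full 28-day screening, the less supported reading. The 12-month contrast is one that no section plans. A ratio above 1 needs two repeats.

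None of this puts the comparison into the analysis text.

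**Conclusion.** The gap is real but modest. A secondary objective stated in both documents has no tabulated contrast in either analysis section, and the nearest available summaries cover unequal time: a ratio of 0.80 against six months, 0.96 after one repeat, and 0.40 against an uncut 12-month history.

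The ratios assume a constant event rate. The comparison with chance also assumes Poisson counts and illustrative rates, since the documents give none. On those assumptions the six-month distortion is smaller than random variation, so the text does not support a conclusion that the plan as written would show a spurious benefit of EZN-2279. The effect is on the interpretation of a descriptive secondary result; the primary endpoint is unaffected.

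A reader might also infer that the crude adverse-event incidence by drug in SAP 7.3 is an error, because exposure is much longer on EZN-2279. It is not: Protocol 13.2.3.5 specifies incidence by number of patients, and SAP 7.2 reports treatment durations. Rates there are an optional improvement.

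**What to change.** **In SAP 6.3.4**, tabulate infections and hospitalisations as counts and as rates per patient-time, using actual days, for two periods:
1. the six months before a stated anchor date, with study entry tied to a date such as the first lead-in dose;
2. the EZN-2279 treatment period, including any repeated weeks.

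Add hospital days where stay dates exist. List within-patient differences, show events between the anchor and the first EZN-2279 dose separately, and footnote that pre-study events were ascertained by history. Keep it descriptive.

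**In SAP 6**, state that the pre-study six months is the comparator for these event outcomes. If the sponsor does not want the comparison, declare in SAP 6.1 that it is dropped.

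**Cost.** SAP wording and a few descriptive columns; no new visits or tests. First confirm that the screening history records event dates and lengths of stay. Protocol 10.3 and 11.1 ask for a 12-month history, but recording of duration is stated only in the general hospitalisation procedure (Protocol 10.5.3.2). If these items are missing, limit the pre-study side to what the history supports.

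**Optional.** In SAP 7.3, show adverse events per patient-time by drug beside crude incidence, using the SAP 7.2 durations, with the treatment period split from maintenance. At an assumed 1 event per patient-year on both drugs, 1 − exp(−days / 365.25) gives crude incidence of 6% in 21 days and 33% in 147 days from exposure alone. The downside is imprecision: six patients for 21 days is 6 × 21 / 30.4375 = 4.14 patient-months, so one lead-in event is 0.24 per patient-month with an exact 95% CI of 0.006 to 1.35.
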